Clinical Study Protocol

Title:

Effectiveness of specific and intensive speech-language therapy on verbal fluency decline and verbal apraxia symptoms in patients with Parkinson's disease with and without Deep Brain Stimulation (DBS) – a randomized single-blind controlled trial.

Acronym: EILT (Evaluation of Intensive Language Therapy)

EKNZ Nr: 2016-01 428

Clinicaltrial.gov. NR: NCT 029 358 42

Document Created: 30.11.2015

Ethical Approval Obtained: 13.09.2016

Study Start/ First Patient IN: 19.09.2016
Last Patient OUT: 29.06.2018

Study End: 22.10.2018

Final Document update: 09.10.2019

Study Synopsis

1. Background and Rationale:	
In the course of Parkinson's disease (PD) speech and language (SL) deficits may often emerge. In addition, severe verbal fluency (VF) decline has been repeatedly observed in the context of deep brain stimulation (DBS) in PD. While PD non-DBS patients have deficits with respect to loudness and intelligibility of their voice, PD patients who have undergone DBS (PD-DBS) tend rather to suffer from difficulties in semantic and phonemic word retrieval, and from speech apraxia symptoms. However, to-date and to the best of our knowledge, therapeutic approaches focusing specifically on SL deficits observed in PD-DBS patients are yet to be developed and evaluated regarding their effectiveness.

2. Objective(s):	
To evaluate the effectiveness of a high frequency and specific SL therapy compared to an unspecific, non-verbal sham intervention (rhythmic balance-mobility-training (rBMT)), as well as to a 'no therapy'-condition.
 
In more detail:
 
 (1) To compare rhythmic speech and gait of PD-DBS and PD non-DBS patients after different intensive rhythmic intervention programs (rSLT, rBMT and no therapy), as well as against healthy controls (HC) directly after the intervention and again in 6 months (short and long-term effects). 
Secondary objectives:
 
 (1) To examine how speech and language abilities alter due to Parkinson Disease's (PD) by comparing PD-DBS, PD non-DBS and HC (all groups are age-, gender and education-matched). (2) To examine the effect of rhythmic interventions on cognitive abilities. (3) To evaluate measures derived from functional Near Infrared Spectroscopy (fNIRS) as a prognostic marker for verbal and cognitive outcome in PD patients with and without DBS over a period of time.
3. Outcomes	
Primary study outcome: rhythmic abilities in speech and gait (Velocity and Cadence).
 
Secondary study outcome:
 
 • Evaluating the effect of rhythmic interventions on cognition. • Evaluating cortical hemodynamic responses in PD and healthy elderly using functional near-infrared spectroscopy (fNIRS)
4. Study Design:	
Investigator-blinded; Randomized; Controlled; Cross-over.

5. Recruitment

Inclusion Criteria for all groups

- a) The patient is able to cooperate
- b) The patient has the mental competence to provide informed consent to participate in the study
- c) The patient speaks and understands German
- d) The participants are aged between 45-80 yrs. old.

Specific Inclusion Criteria for the DBS Group

- a) Fulfilling the above stated inclusion criteria as stated in a, b, c and d above
- b) The patient is responsive to L-DOPA
- c) Having received or being scheduled for DBS

Exclusion Criteria for all groups

- a) Severe psychiatric disease difficult to treat (compulsive disorder, depression, mania, psychosis, anxiety as outlined in ICD-10 (WHO 2015, current version).
- b) Patient with dementia (DMS-V, MMS<24, MoCa <21)
- c) Secondary Parkinsonism
- d) Age ≤ 18 years
- e) Pregnancy (early onset)
- f) Presence of a known disease other than PD that shortens the life expectancy
- g) Mental incompetence to provide informed consent to participate in the study
- h) Previous intracranial surgery
- i) Epilepsy
- j) Contraindications for DBS seen in MRI-scan (malignant tumors, severe micro vascular disease)
- k) Insufficient skills of German language for participating in neuropsychological evaluations
- l) Sensory problems, severe enough to significantly interfere with neuropsychological assessment
- m) Alcohol and/or drug addiction

5.1 Number of Participants with Power Analysis:	The intended sample size of $N_{\text{total}} = 70$ is based on a small effect size ($\eta^2 = .25$, which is statistically significant increase in the elicitation of words within a certain time) and has been calculated via the statistical programme g*power (power analysis published by the University of Düsseldorf). Further, we expect about 5 drop-outs. Thus, the intended total sample size ($N=70$) may compensate for any possible drop-outs, regardless of group type.
--	---

6. Randomization

Group 1+2+3 were randomized 1:1:1. As a cross-over designed study, PD patients could swap groups once a therapy- tranche has successfully been completed (i.e. BL, intensive therapy, 4 weeks Follow-up, 6 months Follow-up assessments), see Figure 1.

Group 4 were healthy elderly, who did not receive any therapy and participated once.

- Group 1: rhythmic Speech language Therapy (rSLT)
- Group 2: rhythmic Balance-Mobility Training (rBMT)
- Group 3: 'Waiting List', PD patients receiving no therapy
- Group 4: Healthy Controls (HC)

[figure not shown]

Figure 1. Study Design

7. Testing

Testing took place at baseline (BL), at 4 weeks (T1, directly after the end of intensive treatment) and at 6 months (T2 Follow-up).

a. Medical Examination (only at Baseline)

- i. Medical Examination regarding PD-dementia
- ii. Drug/Alcohol Abuse
- iii. Weight, Height, BMI
- iv. Medications
- v. UPDRS – Unified Parkinson's Disease Rating Scale-I (1/1)
- vi. Modified Neurologic Examination according to Hoehn & Yahr
- vii. Falls Efficiency Scale-1 (FES-1)

i. Speech-Language Tests with simultaneous PRAAT Recording (BL, T1, T2)

- i. Reading 'the northwind and the sun'
- ii. Aachner Aphasia Test (AAT): Spontaneous speech
- iii. AAT: Repeating
- iv. AAT: Naming

- v. Regensburgerwortflüssigkeitstest (RWT) complete
- vi. Comprehension of language-specific cues (Gardenpath Experiment)

b. Motor Tests

- One-leg and Tandem standing test (timed via chronometric stop watch in seconds)
- Parkinson Orientated Mobility Assessment (POMA)
- Walking 6 Meters (timed and counting steps)

c. Near-Infrared Spectroscopy (NIRS) (only at BL)

d. Neuropsychological tests/ psychiatric questionnaires (BL, T1 and T2)

Neuropsychological Tests:

- i. MOCA – Montreal Cognitive Assessment
- ii. Clock Test
- iii. CERAD – Boston Naming Test
- iv. CERAD – Word Retrieval (Animals)
- v. BVL – Basel Verbal Learning Test
- vi. BVL – Basel Verbal Learning Test
- vii. ROCF - Rey-Osterrieth Complex Figure
- viii. BVL - Basel Verbal Learning Test
- ix. BVL - Basel Verbal Learning Test - Recognition
- x. Word retrieval (S-Words)
- xi. TMT - Trail Making Test A
- xii. Trail Making Test B
- xiii. Stroop Test
- xiv. WMS-R - Verbal Digit Span
- xv. WMS-R - Corsi Blocks
- xvi. Mosaik-Test
- xvii. BVMT-R – Brief Visuospatial Memory Test-Revised
- xviii. TAP – Alertness
- xix. TAP - Divided Attention
- xx. Delayed Recall BVMT-R
- xxi. Recognition BVMT-R
- xxii. Tulia

Psychiatric Self-Rating Questionnaires:

- ii. BDI – Beck's Depression Inventory (1/2)
- iii. BAI – Beck Angst (Fear) Inventar
- iv. MSS – Manie-Selbstbeurteilungsskala (Mania) (1/2)
- v. OCIR – Obsessive-Compulsive Inventory-Revised
- vi. BIS-11 – Barrat-Impulsiveness-Scale (1/2)
- vii. PDQ-39 – Parkinson Quality of Life Questionnaire
- viii. NEO-FFi-30 Items

- ix. AES-S – Apathy Evaluation Scale
- x. PFS-16 – Parkinson-Fatigueskala
- xi. Lebensqualitätsfragebogen (SeiQoI-DW)
- xii. IQ-Code – Questionnaire of cognitive abilities in elderly

8. Interventions

No drugs involved. While speech-language therapy is an established intervention programme in clinical and therapeutic practices, the rhythmic balance-mobility-training (rBMT) has been developed specifically to prevent mobility and balance issues in PD patients and has been evaluated scientifically (see *Parkinson Schweiz* <http://www.redance.ch/page/wirkung/sturzpraevention.html>).

Note that whether or not DBS is performed on a patient is dependent on multiple criteria and can only be decided by the medical team consisting of neurologists, neurosurgeon and neuropsychologists/ psychiatrists. Whether or not DBS is performed on a patient is not part of the study, as it is a normal medical procedure to cure dyskinesia and other motor symptoms arising in Parkinson's disease.

rSLT	
Contents	
 I. 3x 45 Minute sessions per week II. Empathic relationship between patient-therapist III. Specific exercises for the perception and improvement of respiration, phonation, articulation and body posture IV. Rhythmic Exercises according to 'Accent Method' by Sven Smith (1935, 1976)

rBMT	
Contents	
 • 3 x 45 minute sessions per week. • per session: at least 10 songs had to be danced, each with a length ranging from 1:47 - 3:25 Minutes per song. • 1st Week: Level 1. • 2nd Week: Level 1+2. • 3rd Week: Level 2. • 4th Week: Level 2+3.

7. Statistical Analysis

To calculate group differences (i.e. rSLT, rBMT, NT, HC) several univariate ANOVA with post-hoc Bonferroni corrections were performed.

Relationships between speech and gait variables were computed with Spearman's correlations (significance level $p < .05$). The level of statistical significance was set at $p < .05$.

Changes in performance were analyzed with the reliable change score (RC). According to Jacobson and Truax (1991) scores are compared on a participant-individual level (e.g. BL with 4 weeks FU, and BL with 6 months FU). Positive scores indicate an improvement in performance, and negative scores indicate a worsening of performance. The RC shows whether a difference in performance is statistically significant on the basis of the reliability of the measurement. Thus, the reliable change score is equivalent to computing a z-score based on standard deviation units.

Further group comparisons are based on the RC scores. All statistical analyses were conducted with SPSS and R. All results are presented with effect sizes.

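### The detailed primary objective names DBS and non-DBS patients, but the stated analysis specifies no DBS comparison, so that part of the objective is not answered

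*Combined protocol and SAP*

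**What the plan says.** Section 2, Objective(s), opens with a therapy question: "To evaluate the effectiveness of a high frequency and specific SL therapy compared to an unspecific, non-verbal sham intervention", and also against no therapy. The detailed primary objective beneath it brings in DBS status: "To compare rhythmic speech and gait of PD-DBS and PD non-DBS patients after different intensive rhythmic intervention programs". The first secondary objective is to be met "by comparing PD-DBS, PD non-DBS and HC (all groups are age-, gender and education-matched". The background in section 1 explains why DBS status is of interest. Non-DBS patients are described as having problems of loudness and intelligibility, whereas DBS patients "tend rather to suffer from difficulties in semantic and phonemic word retrieval, and from speech apraxia symptoms".

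Section 6, Randomization, gives the allocation as "Group 1+2+3 were randomized 1:1:1" and mentions no stratification factor. It adds that "PD patients could swap groups once a therapy- tranche has successfully been completed", and points to Figure 1, which is not available here.

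The Statistical Analysis section states: "To calculate group differences (i.e. rSLT, rBMT, NT, HC) several univariate ANOVA with post-hoc Bonferroni corrections were performed". On reliable change (RC) scores it says only: "Further group comparisons are based on the RC scores". It mentions no DBS factor, covariate, interaction or subgroup.

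Section 5, Recruitment, admits to the DBS group both patients already treated with DBS and patients awaiting it. Section 5.1 sets a total of 70 with about 5 drop-outs. It gives no number of DBS patients and does not say whether the healthy controls are counted in the 70.

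**The concern.** An objective that names two patient types under three therapy conditions needs an analysis containing both factors. The listed ANOVA has one factor, with levels rSLT, rBMT, no therapy and healthy controls. A reader of the results would learn whether the arms differ in a mixed PD population. They would not learn whether DBS and non-DBS patients differ after therapy, or whether the therapy effect differs between them. The background presents the lack of therapy aimed at DBS patients as the gap the trial addresses, so this is a substantial part of its purpose.

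A lesser issue is that, without stratification or adjustment, the arms may differ by chance in their share of DBS patients. If DBS status affects change over the follow-up, the realised contrast moves and its standard error is larger than necessary.

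**Working it through.** **1. Objective against analysis**

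| Comparison named in section 2 | Matching analysis in Statistical Analysis |
|---|---|
| rSLT vs rBMT vs no therapy | Yes, ANOVA by therapy group |
| PD-DBS vs PD non-DBS under the three conditions | None specified |
| PD-DBS vs PD non-DBS vs healthy controls (first secondary objective) | None specified |

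**2. The plan's own figure.** The only planning number is N = 70. Power, test family and number of groups are not stated, so it cannot be uniquely reproduced. Taking eta-squared = .25 literally, f² = .25/.75 = .333. A one-way ANOVA then needs 33, 42 or 50 patients (three groups) or 37, 47 or 56 (four groups) at 80, 90 or 95% power. Adding 5 drop-outs gives at most 61. A six-group one-way ANOVA at 95% power gives 66 + 5 = 71, which is close to 70 but rests on unstated inputs. The figure therefore does not show whether a DBS comparison was planned for.

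**3. Chance imbalance if allocation was unstratified.** Assumed inputs: all 70 are PD patients (arms 24/23/23), or about 52 are PD if a quarter of the 70 are healthy controls (70 × 3/4 = 52.5; arms 18/17/17). DBS share is taken as 20, 30 or 50%. With the DBS total fixed, the probability that some two arms differ by at least 20 percentage points is:

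| PD patients | 20% DBS | 30% DBS | 50% DBS |
|---|---|---|---|
| 70 | .22 | .31 | .33 |
| 52 | .29 | .42 | .42 |

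**4. What such an imbalance would do.** Shift in the realised contrast = difference in DBS share × DBS effect d on the analysed score. For a 20-point difference this is .20 × .5 = .10 SD, or .20 × .8 = .16 SD. For scale, the standard error of an arm contrast with 23 per arm is √(2/23) = .29 SD. The share of residual variance removed by a DBS term at 50% DBS is .25d²/(1 + .25d²): .0625/1.0625 = 5.9% at d = .5, and .16/1.16 = 13.8% at d = .8. These values of d are assumptions. In simulations of the unadjusted three-arm ANOVA (51 or 69 patients, 50% DBS, d = .5 or 1), type I error was .047 to .052 and the mean contrast error was essentially zero.

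**5. Precision of the missing comparison.** For the 3 × 2 interaction, df1 = 2 × 1 = 2. With 70 − 5 = 65 patients, df2 = 65 − 6 = 59. Noncentrality is f²N with f² = η²/(1 − η²).
- η² = .06: f² = .064, noncentrality 4.1, power .41.
- η² = .14: f² = .163, noncentrality 10.6, power .82.

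With only 52 PD patients, power is .33 at f = .25 (η² = .059) and .71 at f = .40 (η² = .138).

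For one pair of arms of size n with DBS share p, the therapy contrast has variance 2σ²/n. The DBS difference in that contrast has variance 2σ²/[n·p(1 − p)]. The ratio of standard errors is 1/√[p(1 − p)]: 2.0 at 50% DBS, 2.2 at 30% and 2.5 at 20%.

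**The case against.** The lead objective is a therapy contrast, and the listed ANOVA does address it. The detailed objective can be read as comparing programmes among PD patients of both types, which would suit the title, rather than as a therapy-by-DBS question. The plan also refers to several ANOVAs and to further comparisons of RC scores, any of which might involve DBS status. This part of the objection stands: a reader might infer that the whole primary question goes unanswered, but only its DBS part does. It does not remove the point, because unnamed comparisons are not a specification, and the first secondary objective names both patient types without a matching analysis.

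A reader might also infer that randomisation ignored DBS status. The text does not settle that: it states no stratification, and Figure 1 might show strata. Stratified allocation would still leave the DBS comparison unspecified.

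A further tempting inference is that DBS imbalance biases the arm contrasts. In the randomised first tranche it does not do so systematically, because 1:1:1 allocation balances DBS share on average and the test keeps its level. Data gathered after a swap differ, since the swap is not said to be randomised.

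Finally, DBS status should not be called a known strong predictor of the analysed outcome. The background describes different kinds of speech deficit. It gives no effect on change in rhythmic speech, velocity or cadence, and stable level differences largely drop out of change from a patient's own baseline. Nor do the documents plan separate significance tests within each patient type.

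**Conclusion.** The mismatch holds: the detailed primary objective and the first secondary objective name DBS and non-DBS patients, and no stated analysis compares them. The overall therapy question is addressed; its DBS part is not. This conclusion follows from the text alone and needs no numerical assumption.

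The consequence for the therapy contrasts is smaller and conditional. If allocation was unstratified, a DBS imbalance of 20 points or more between some two arms has probability of about .22 to .42, under the assumed 52 to 70 PD patients and 20 to 50% DBS. It then shifts the realised estimate and costs precision only if DBS status affects the change score, and the documents give no figure for that effect. Severity: should fix.

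**What to change.** In the PD patients of the randomised first tranche, fit therapy (rSLT, rBMT, no therapy) + DBS status at baseline + baseline score. Report the DBS-adjusted therapy contrasts. Then add the therapy-by-DBS interaction and report its estimates with confidence intervals, labelled as imprecise. Specify separately the comparison of DBS patients, non-DBS patients and healthy controls that the first secondary objective requires. If no DBS comparison is intended, the objectives should be reworded to say so.

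Fix DBS status for the analysis at baseline as implanted yes or no, because the DBS group also includes patients only scheduled for the procedure, whose status could change within six months. The eligibility text must be reconciled first: section 5 excludes earlier intracranial surgery in all groups, yet admits patients who have already had DBS.

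Report DBS counts per arm and state whether allocation was stratified by DBS.

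The cost is 1 degree of freedom for the DBS term, or 3 with the interaction. No new patients or visits are needed. The drawback is that the interaction will be estimated with limited precision, so a non-significant result must not be read as equal response in the two patient types.

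### Title and sample size concern verbal fluency, but the primary outcome is rhythm in speech and gait, and neither outcome list names fluency or apraxia

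*Combined protocol and SAP*

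**What the plan says.** The title announces "Effectiveness of specific and intensive speech-language therapy on verbal fluency decline and verbal apraxia symptoms". The background section argues from the same deficits: falling fluency, impaired word retrieval and speech apraxia, particularly after deep brain stimulation.

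The detailed objective in section 2 is different: "To compare rhythmic speech and gait of PD-DBS and PD non-DBS patients after different intensive rhythmic intervention programs". Section 3 follows that objective and gives "Primary study outcome: rhythmic abilities in speech and gait (Velocity and Cadence") as primary. Its secondary outcomes are "Evaluating the effect of rhythmic interventions on cognition" and cortical fNIRS responses.

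Section 5.1 bases a total of 70, with about 5 drop-outs expected, on an effect described as a "statistically significant increase in the elicitation of words within a certain time".

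The Testing section includes "Regensburgerwortflüssigkeitstest (RWT) complete" in the speech-language battery at baseline, T1 and T2. It also places two shorter word-retrieval tasks (animals and S-words) among the neuropsychological tests.

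The cover dates give last patient out as 29.06.2018 and study end as 22.10.2018, and then "Final Document update: 09.10.2019".

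**The concern.** A confirmatory trial needs its claim, its primary endpoint and its sample size to refer to the same quantity. Here the claim in the title and the sizing share one quantity (fluency), while the objective and the primary outcome share another (rhythm and gait).

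Two things are at stake. First, a reader who sees N = 70 with a power analysis will assume that the primary result was powered, yet nothing in the document supports that for speech rhythm, velocity or cadence. Second, a reader who sees the title will expect a designated test of fluency and apraxia, and there is none. Any fluency result would come from an unranked measure, selected from at least three available tests.

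The late update date adds to this. If the outcome list was settled before data were available, the mismatch is one of labelling. If it was not, the primary p-values do not carry their nominal meaning. The document gives no way to tell which is the case.

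**Working it through.** **Step 1: set the statements side by side.**

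| Place | Quantity named |
|---|---|
| Title | verbal fluency decline, verbal apraxia |
| Section 2, detailed objective | rhythmic speech and gait |
| Section 3, primary | rhythm in speech and gait, velocity and cadence |
| Section 3, secondary | cognition (no test named), fNIRS |
| Section 5.1, sizing | words elicited in a set time |
| Testing section | RWT at baseline, T1, T2; animals; S-words |

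Rows 2 and 3 agree with each other. Rows 1 and 5 agree on fluency. The two pairs do not meet, and the secondary outcomes do not name fluency or apraxia either.

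**Step 2: try to reproduce N = 70.** The inputs are η² = .25 (section 5.1), significance level .05 (Statistical Analysis section), N = 70, and three randomized groups, or four with healthy controls (section 6). Power and the test are not stated. I assume a one-way ANOVA and try 80, 90 and 95% power.

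- Effect size read literally: f = √(η²/(1 − η²)) = √(.25/.75) = 0.577.
- Power = P(F′ > F critical), with k − 1 and N − k degrees of freedom and noncentrality λ = f²N.
- With f = 0.577, N = 70: λ = 0.333 × 70 = 23.3. Power is 99.2% for three groups and 98.5% for four.
- If .25 was meant as f: λ = 0.0625 × 70 = 4.375. Power is 43% for three groups and 37% for four.

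| Reading of .25 | Groups | N at 80 / 90 / 95% power |
|---|---|---|
| η² | 3 | 33 / 42 / 51 |
| η² | 4 | 40 / 48 / 56 |
| f | 3 | 159 / 207 / 252 |
| f | 4 | 180 / 232 / 280 |

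None of these gives 70, or the 65 left after 5 drop-outs. Some unstated combinations come close. For example, a group-by-time interaction with f = .25, three groups, two time points, an assumed correlation of .5 and 95% power gives 66; with four groups and 90% power it gives 64. The document selects none of them.

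**Step 3: apply the sizing to the stated primary.** This cannot be done. No effect size, standard deviation or power is given for speech rhythm, velocity or cadence, so neither a required N nor a power can be computed for them.

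**Step 4: dates.**

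- 29.06.2018 to 09.10.2019: 365 days to 29.06.2019, plus 102 = 467 days.
- 22.10.2018 to 09.10.2019: 365 − 13 = 352 days.

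The randomization and analysis sections are in the past tense, while the risk section partly keeps the future tense. So some text was probably edited late, but this does not show which content changed.

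**The case against.** The strongest reply is that the primary outcome is not an orphan. It matches the detailed objective, the rhythmic content of both interventions and the planned speech–gait correlations. That stands: the conflict is with the title and the sizing, not with the objectives.

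A second reply is that fluency may be covered by the secondary outcome on cognition, since the animal and S-word tasks are listed with the neuropsychological tests. This is possible, but no test is named there, and the RWT is listed with the speech-language tests. Secondary objective 1 does mention speech and language abilities, but as a comparison of patient types with healthy controls, not as a treatment effect.

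Three stronger readings are tempting, and the documents do not support them:

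- **The primary was switched after the data were seen.** A last-update date does not show this. The document was created on 30.11.2015 and had ethics approval on 13.09.2016, and the present primary may date from then.
- **The confirmatory claim rests on gait alone.** The primary covers speech as well. The parenthesis may qualify gait only or both, and recorded speech tasks are scheduled at every visit. The fair criticism is that no speech-rhythm measure is named.
- **The RWT at T1 should now become primary.** Doing so after study end would be a definite post-hoc change made to cure a possible one. It would also omit apraxia and the long-term comparison in the stated objective, and the power calculation for words cannot be reproduced either.

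**Conclusion.** The mismatch is real and rests on the text alone. The title and the only sample-size basis concern verbal fluency; the primary outcome does not; and fluency and apraxia have no place in either outcome list. It follows that N = 70 does not size the stated primary and that the titled effectiveness claim has no designated endpoint.

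The loss of power for the primary cannot be quantified, because no inputs are given. The range in the working (43% to 99.2% for three groups) describes the two readings of the fluency effect size under an assumed one-way ANOVA. It says nothing about rhythm or gait.

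On timing, the conclusion is limited: with a final update 467 days after last patient out and no version history, prespecification of the primary cannot be shown from this document. Nor does the document show the opposite. A reader might also infer that the trial can say nothing about fluency. That goes too far, because the data exist at three visits and can be analysed. What is missing is their rank.

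**What to change.** 1. State the version and date at which the primary outcome was set. Treat as confirmatory only what a version dated before data were available designates, and report everything else as exploratory.
2. State in section 5.1 that the N = 70 power statement applies to word elicitation and not to speech rhythm, velocity or cadence.
3. List RWT verbal fluency as a named outcome in section 3, specifying the score used. Rank it as in the earliest dated version; if that version is silent, rank it as secondary or exploratory. Do not make it primary after the fact.
4. Unless a pre-data version designates fluency and apraxia endpoints, remove both terms from the confirmatory effectiveness claim.

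The work consists of retrieving earlier versions and revising text; the RWT is already scheduled at baseline, T1 and T2, so no new data are needed. The price lies in interpretation: the stated power basis no longer supports the primary result, and some results may lose confirmatory status.

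### Cognition is a secondary objective with no named score or time point, and no correction spans its roughly 30 to 34 tests, so chance findings are likely to far exceed 5%

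*Combined protocol and SAP*

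**What the plan says.** - **Objective and outcome.** Secondary objective (2) in the Study Synopsis is "To examine the effect of rhythmic interventions on cognitive abilities". The matching entry in section 3 (Outcomes) is "Evaluating the effect of rhythmic interventions on cognition". Neither names an instrument, a domain score, a composite or a main time point.
- **Assessments.** Item d of section 7 (Testing) is headed "Neuropsychological tests/ psychiatric questionnaires (BL, T1 and T2" and lists 22 neuropsychological rows. The follow-ups are "at 4 weeks (T1, directly after the end of intensive treatment) and at 6 months (T2 Follow-up".
- **Group tests.** Section 7 (Statistical Analysis) says that "several univariate ANOVA with post-hoc Bonferroni corrections were performed". The family covered by the Bonferroni correction is not defined.
- **Threshold.** The same section adds: "The level of statistical significance was set at $p < .05".
- **Change scores.** For the reliable change score, "scores are compared on a participant-individual level (e.g. BL with 4 weeks FU, and BL with 6 months FU". Further group comparisons then use these scores, and effect sizes are promised for all results.
- **Correlations.** "Relationships between speech and gait variables were computed with Spearman's correlations (significance level $p < .05". No count of variables or visits is given.

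The documents give no testing order for the cognitive tests, no correction across tests or follow-ups, and no exploratory label.

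**The concern.** A post-hoc Bonferroni step after an ANOVA ordinarily protects the pairwise group comparisons within that one ANOVA. It does nothing about running the same ANOVA on many cognitive tests at two follow-ups. With no endpoint named, any listed test at either visit could be put forward as the answer to the cognition objective after the results are seen. A reader of the final report could not tell a real effect from the one or two chance results that a battery of this size is expected to produce. The speech-gait correlations share the gap, since each is judged at 5% with no stated correction.

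**Working it through.** The plan states no family-wise error rate, so there is no figure of its own to reproduce. The only error figure is 5% per test.

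**Inputs from the documents**
- Level per test: 0.05.
- Listed rows: 22. Merging the four BVL rows into one and the three BVMT-R rows into one gives 22 − 3 − 2 = 17 tests. Treating Trail Making A and B as one gives 16, and also treating the two TAP tests as one gives 15.
- Follow-ups: 2.
- Groups with change scores: 3. Healthy controls took part once.

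**Assumptions**
- Every listed test is analysed at both follow-ups, and no test has a true effect.
- Arm sizes are 22 (65 completers ÷ 3 ≈ 22, if all are patients) or 17 (70 ÷ 4 ≈ 17, if healthy controls are included in the 70).
- Correlations are not in the documents and are varied.

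**Number of comparisons.** 15 × 2 = 30; 17 × 2 = 34; 22 × 2 = 44.

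**Expected false-positive ANOVAs** (m × 0.05, whatever the correlation). 30 × 0.05 = 1.5; 34 × 0.05 = 1.7; 44 × 0.05 = 2.2.

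**Chance of at least one, if independent** (1 − 0.95^m). m = 30: 78.5%; m = 34: 82.5%; m = 44: 89.5%.

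**Chance of at least one, if correlated, 34 tests** (simulation under no effect, 3,000 or more runs in most settings, Monte Carlo error about one percentage point). Model A has 22 per arm and one common correlation among all 34 scores. Model B has 17 per arm, the stated correlation between instruments, and 0.5 or 0.7 between the two follow-ups of one instrument. The last two columns require a significant ANOVA plus a Bonferroni-significant contrast of either therapy with no therapy.

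| Correlation | Any ANOVA, A | Any ANOVA, B | Therapy vs none, A | Therapy vs none, B |
|---|---|---|---|---|
| 0 | 83% | 78–81% | 64–65% | 61–64% |
| 0.3 | 70% | 70–71% | 53–54% | 53–54% |
| 0.5 | 55–58% | 59–60% | 40–41% | 44–45% |
| 0.7 | 38% | 43–47% | 26–27% | 30–35% |

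With all 44 rows, Model A gives about 61% for any ANOVA at correlation 0.5 and 41% at 0.7.

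**With a correction.** Bonferroni over 34 tests sets 0.05 ÷ 34 = 0.00147 per test and holds the family rate at or below 5%. Benjamini-Hochberg over the same family, with no true effect anywhere, gave a chance of any false positive of about 5% or less in simulation.

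**Speech-gait correlations.** The number of coefficients is not given, so no error rate can be computed for them.

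**The case against.** The best defence is that the plan promises little about cognition. The wording is to examine and to evaluate. The analysis section speaks of several ANOVAs without saying that every listed row is tested. No sentence says that a single significant test would settle the objective. The scope of the Bonferroni correction is undefined, so a wider scope is not strictly excluded. Effect sizes are already promised, and the primary outcome is untouched.

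Much of this stands. Running the whole battery is an inference from an undefined outcome, and the percentages depend on it. A reader might also infer that a false claim of a therapy effect on cognition is more likely than not. The documents do not support that. The contrast that would carry such a claim falls below 50% at a correlation of about 0.4, and even the any-ANOVA figure falls below 50% between 0.6 and 0.7.

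The correlation argument also runs the other way. Group comparisons use change scores, and subtracting baseline removes whatever the tests share through a stable trait. One simulation assumed raw correlation 0.5 arising only from such a trait, retest correlation 0.7 and 17 per arm. It gave 81% for any ANOVA and 63% for therapy against no therapy. With 30% of the visit-specific variance also shared, these became 73% and 55%. Those inputs are assumptions too, so they do not settle the matter.

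The defence does not supply a named endpoint, a stated correction across tests or an exploratory label.

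**Conclusion.** The gap is real and should be closed. Under the rule as written, and if the listed battery is tested with no true effect, the chance of at least one false-positive ANOVA in 34 tests runs from about 83% (independent) through 55–60% (correlation 0.5) to 38–47% (0.7). For a Bonferroni-significant contrast of a therapy with no therapy the corresponding figures are about 61–65%, 40–45% and 26–35%. Every value is several times the nominal 5%.

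The results rest on three assumptions: all tests are run at both follow-ups, the correction covers only group contrasts, and the correlation lies within the range shown. Because the documents give no correlation, a single probability or a statement about which side of 50% it falls on is not justified. The correlations between speech and gait have the same omission, but without an error rate that can be stated. The point concerns a secondary objective and leaves the primary outcome unaffected.

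**What to change.** In section 7 (Statistical Analysis):

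- Treat all cognitive tests at T1 and T2 as one family and state how many tests were run.
- Report Benjamini-Hochberg adjusted p-values over that family, with effect sizes and 95% confidence intervals.
- Label the single-test cognitive results and the speech-gait correlations as exploratory.
- Base no conclusion about cognition on an unadjusted p-value below .05.

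A composite cognitive score may be added only if it is disclosed as specified after data collection. The last patient left on 29.06.2018 and the document was last updated on 09.10.2019, so it cannot be presented as prespecified.

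The cost is wording and a recalculation on data already collected. The downside is that an isolated single-test cognitive result can no longer be claimed.
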